The study will be conducted within three SNFs in New York City, The New Jewish Home, Terence Cardinal Cooke Health Care Center, and the Mary Manning Walsh Home. The study will be conducted in three urban SNFs with the goal of enhancing resident sleep quality, mood, anxiety, pain, cognitive performance, and activity engagement. None of the SNF will be engaged in the study related procedures. All procedures will be performed by the NYULMC IRB approved personnel.

Figure 2. Sources (%) of Sleep Disruption

Design: This is a 4-year stepped wedge intervention trial (SWT) in six SNF units within three SNFs (two units/SNF, Figure 3). In a SWT, all clusters (here, SNF units) receive the intervention but at different time points.⁷⁶ The stepped wedge design is a useful alternative to a parallel cluster trial with multiple advantages, including: 1) increased efficiency, 2) requirement for fewer research staff (thereby reducing costs) due to sequential rather than parallel intervention testing for each cluster, 3) more observations, with each cluster serving as its own “control”, and 4) ultimately greater power for a given same sample size when the intra-class

correlation is high.⁷⁷ There will be no engagement of the second unit within each facility prior to their scheduled engagement and facilities randomized to later allocation will wait for the intervention. In place of an “attention control,” [name] will provide all unengaged facilities with quarterly geriatric education offerings to avoid loss of interest while waiting for the sleep improvement program. In

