SLUMBER, every unit provides baseline and follow-up data. We will collect baseline data just prior to the intervention on a given unit and within 1 month after a 3-month exposure to the SLUMBER program. Facilities will encourage staff to continue to use intervention approaches after the 3-month intervention period. We will collect additional follow-up sleep and activity data with resident surveys and repeat wrist actigraph measures 3 and 6 months after the post-intervention period for all units to test for increased or continued benefit (sustainment) over time and assess for the possibility of reduced benefits over time (relapse). **From the intervention beginning and throughout the remaining study duration, real-time environmental data (noise via decibel meters) and observed sleep disturbance (by staff anonymous recording of sleep disturbances) will be available to SNF staff on a visible computer interface (described below) to facilitate continued use of SLUMBER strategies.** MDS 3.0 data collection will provide repeated measures of mood, cognitive function, and physical function for the full study duration (Figure 3). We selected a 3-month follow-up time point to strike a balance between sufficient time for intervention effects to emerge while considering the rapidly changing health status of LTC residents. Also, MDS data are collected quarterly and the intervention itself includes an initial mentoring session, three additional meetings over the next two months, and a follow-up session at the end of three months.

Supplement Design:

1. Overview: For this supplement application, we propose a 12-month intervention trial focused on dementia care SNF units using a modified comprehensive sleep improvement program, SLUMBER-RD, which is a mentored approach for unit staff. The study will be conducted in two urban SNFs with the goal of enhancing sleep quality, mood, cognitive performance, and activity engagement.

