all residents by using Evaluation to Consent assessment tool (Appendix 9). [name] will be available to make final determinations related to capacity to consent for participants based on the information collected with Evaluation to Consent tool , For those residents indicating a wish to participate but who are unable to demonstrate capacity, the Research Assistant will notify the facility to approach legal surrogates with an informational letter and self-addressed, stamped postcard to indicate a willingness or refusal to receive a phone call where the research assistant will explain the study and request consent for that resident to participate (see Appendix 2 and F. Subject Identification, Recruitment and Consent/Assent). Due to the time sensitive nature of the research, any surrogate who does not return the postcard within 10 days from postmark will be called by a Research Assistant. Verbal consent will be obtained via the phone (see Appendix 3 Surrogate Verbal Consent). Consent will be for agreement to wear a wrist actigraph, observation, and provide brief interview responses at baseline, post-intervention, and at 3 and 6-month follow-up. Our procedure to assess capacity to consent for research has been used in several prior studies. We note that even some patients with moderate levels of cognitive impairment have the capacity to consent and we will use standardized IRB-approved protocols for conducting this capacity assessment.

Inclusion criteria for residents are: 1) living in the unit of intervention, 2) ability to communicate and follow simple commands, 3) English- or Spanish-speaking, and 4) capacity to consent assessed with standard questions used to assess capacity or having a surrogate who can provide consent.

consent on each unit during the baseline pre-intervention period from all residents. Severely demented residents do not reside in the units chosen for the SLUMBER intervention; however, we anticipate some residents will have some level of cognitive impairment. [name], (a cognitive and capacity specialist) will train research assistants in the methods of capacity assessment).

Research assistants will assess capacity for

SLUMBER Protocol V.8/27/2018

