Analysis of Scheduled Study Assessments: Mixed-effects models will be used to assess improvement in sleep outcomes due to the SLUMBER intervention. When applied to repeated measures designs, mixed-effects models accommodate incomplete data across time points (e.g., due to resident death) and can permit specification of a wide variety of residual covariance structures.¹⁰³ Each outcome will be analyzed using a two-level mixed-effects model with time as a fixed factor having four levels (baseline, post-intervention, 3-months, and 6-months), and residents nested within SNF units. We will also conduct a sensitivity analysis that takes into account nesting of units within facilities. Non-independence of residuals across time will be modeled using a variety of covariance structures (e.g., unstructured, compound symmetric, autoregressive) by selecting the covariance structure that provides the best fit (according to the Bayesian Information Criteria). We will assess the primary hypothesis concerning the intervention effect by comparing the average baseline score to the average post-intervention and 3-month scores. We will test the secondary hypothesis concerning withdrawal of the intervention by comparing the 3-month to 6-month data.

Analysis of Routinely Collected Measures: Routinely collected measures (for all consented residents on intervention units) will be analyzed using a three-level model in which time is nested within resident and residents are nested within SNF units.¹⁰⁴ A sensitivity analysis will consider a model in which a fourth level of

Level 1 (time) Outcome _{ijk} = $\pi_{0jk}+\pi_{1jk}(\text{Intv})+\pi_{2jk}(\text{IntvQtr})+e_{ijk}$	units nested within facilities is considered. The three-level model will include two key time varying predictors: Intv ,

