For the analysis of routinely collected measures, the primary outcome concerns the test of the average of measures prior to the implementation of the intervention compared with the average of the measures after the implementation of the intervention. Using six steps in the stepped wedge design, the detectable standardized effect associated with the introduction of the intervention (the primary hypothesis) was computed as a function of the *final* sample size within each unit (columns) and the intra-cluster correlation (rows) shown in Table 7⁷⁷. All conditions specified have the ability to detect a medium or smaller effect ($< .50$). The smallest *final* sample size of N=10 provides sufficient power to detect an effect of 0.60 or smaller. Referring to Table 5, we see that all combinations of consent rate and attrition rate yield a *final* sample size of 10 or larger. Based on the results of Tables 7 and 5, the analyses for the routinely collected measures will have sufficient power to detect a clinically meaningful effect (i.e., a standardized effect of .60 or smaller).

Threats to Internal Validity: If outcomes improve with SLUMBER, we will consider explanations alternative to the treatment effect. While unlikely, residents may improve over time unrelated to the SLUMBER intervention. Use of routinely collected measures (MDS) will be investigated to identify possible improvements prior to the introduction of the intervention. MDS measures will also counterbalance the influence that the act of measuring has on the outcome since these measures are collected within routine care. Individuals with poorer outcomes might withdraw due to refusal, discharge or death, thereby creating an illusion of improvement. We will test for systematic attrition by comparing baseline scores of those who withdraw to those who remain. The stepped wedge design staggers introduction of the intervention to mitigate this threat. Spillover training and effects from one unit to the next unit in the same facility not yet engaged are also possible. We will include “manipulation checks” measuring intended changes between units (e.g., noise reductions) to assess whether contamination of sleep strategies occurred in the second unit at a facility before introducing SLUMBER to that unit.

C7. Data Storage and Confidentiality

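### Staggered starts do not protect the primary contrast from selective attrition, and the baseline-score check cannot separate harmful from harmless dropout or size the bias

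*Combined protocol and SAP*

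**What the plan says.** The threat is stated plainly in C6, Threats to Internal Validity: "Individuals with poorer outcomes might withdraw due to refusal, discharge or death, thereby creating an illusion of improvement". Two responses follow. One is a check: "We will test for systematic attrition by comparing baseline scores of those who withdraw to those who remain". The other is a design claim: "The stepped wedge design staggers introduction of the intervention to mitigate this threat".

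Other sections fix when residents are seen. A5 (Design): "We will collect baseline data just prior to the intervention on a given unit". C1, Step B: the team will seek "consent on each unit during the baseline pre-intervention period from all residents". A5 again, on waiting units: "There will be no engagement of the second unit within each facility prior to their scheduled engagement". Under C1, Step C and C6, MDS data cover consented residents only, starting from the last record before launch.

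The primary analysis (C6, Analysis of Scheduled Study Assessments) is a mixed model with four time levels counted from each unit's launch and no stated calendar-period term. The primary test sets baseline against the average of the post-intervention and 3-month scores. The model is said to cope with incomplete data, including data lost to death. No analysis allowing for missing-not-at-random dropout is stated.

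**The concern.** Staggering could help against selective attrition if some consented residents were followed, and lost, while still unexposed; their attrition would show what happens without the intervention. Here no consented cohort is followed for any length of time before launch. Baseline cells carry almost no attrition and follow-up cells carry essentially all of it, in all six units.

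The baseline comparison is then the only stated safeguard, and it looks at the variable whose influence on dropout the mixed model already accommodates. What can bias the contrast is dropout related to outcomes that were never observed. The primary test is before-after with no parallel control, so such bias does not cancel. At the attrition the plan allows for, about 30 to 48 of 120 residents (25-40% of 6 × 20) would leave.

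**Working it through.** **The plan's own figures.** Table 5 is 40 × consent × (1 − attrition), rounded down: 40 × 0.50 × 0.75 = 15; 40 × 0.60 × 0.60 = 14.4, shown as 14. All 16 cells match. Table 6 at 14 per unit and ICC .20 gives 0.57. I obtain 0.573 as (1.96 + 0.84) × SE from a generalised least squares model with six staggered units, each measured once before and twice after launch, and calendar-period effects. All 25 cells agree within 0.01. No stated figure is wrong on this point, and the layout that fits has only one pre-launch measurement per unit.

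**Does staggering help?** Let attrition shift the estimated means by b1 at post-intervention and b2 at 3 months; at baseline the shift is about 0. The stated contrast carries (b1 + b2)/2 in every unit, so start order drops out.
- b1 = b2 = 0.20: bias (0.20 + 0.20)/2 = 0.20. Calendar-period terms leave this unchanged at 0.20.
- b1 = 0.10, b2 = 0.20: bias 0.15. A model with calendar terms would carry 0.14 at ICC 0, falling to 0.06 at ICC 0.4, but that is not the stated primary model.

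**How large might b1 and b2 be?** Inputs from the documents: 20 per unit (B1) × 6 units = 120; 25-40% attrition (Table 5); a 0.60 SD target (C6). Assumed, because the documents do not give them: correlation r between adjacent visits of .3-.7 with first-order autoregressive decay; dropout odds ratio (OR) of 2-3 per SD worse; attrition spread evenly over the two intervals to 3 months; true effect zero; unit clustering ignored.

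Take dropout driven by the part of the change since the last visit that earlier scores do not predict. With per-interval dropout p = 1 − √(1 − a) for total attrition a, and κ = ln OR / √((ln OR)² + π²/3), a close approximation is

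bias ≈ κ × φ(z_p)/(1 − p) × √(1 − r²) × (1 + r/2),

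where z_p is the normal quantile cutting off p, and the last factor averages the two follow-ups (the first-visit bias carries forward as r times itself).
- Low end (a = 25%, OR 2, r = .7): p = 0.134, κ = 0.357, φ/(1 − p) = 0.249. Bias ≈ 0.357 × 0.249 × 0.714 × 1.35 = 0.086.
- High end (a = 40%, OR 3, r = .3): p = 0.225, κ = 0.518, φ/(1 − p) = 0.388. Bias ≈ 0.518 × 0.388 × 0.954 × 1.15 = 0.22.

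Simulation with the likelihood estimate for monotone missing data gives 0.09-0.23 SD, or 15-38% of 0.60 (0.09/0.60; 0.23/0.60).

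**What would the baseline check show?** Two-sample t test at 5%, N = 120, same assumptions:
- Dropout on the last observed score: bias about 0; the test rejects in about 60-100% of trials.
- Dropout on unpredicted change: bias 0.09-0.23 SD; the test rejects in about 5%.
- Dropout on current level: the test rejects in about 10-89%, depending mainly on r.

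A second set of assumptions (r of .5 and .7; correlation of .5 or .8 between dropout propensity and the score component driving it) gives the same pattern: last observed score, bias about 0 and 95-100% rejection; unpredicted change, 0.10-0.31 SD and about 5%; current level, 0.07-0.27 SD and 65-100%.

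If the raw difference since the last visit drives dropout instead, its correlation with the score it is measured from is −√((1 − r)/2), that is −0.59 at r = .3 and −0.39 at r = .7. The test can then reject, but with leavers looking better at baseline, the reverse of how they fared.

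**The case against.** **The check is not blind.** A reader might infer that the baseline comparison always misses biasing dropout. It does not. The plan's wording about poorer outcomes is closest to dropout on current level, and there the test often rejects. What remains is that it rejects as readily when bias is zero, has variable power, and gives no size.

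**The mixed model covers more than baseline.** A reader might infer that any dropout related to how residents fared after baseline biases the result. Dropout explained by an observed post-intervention score is missing at random and gives bias near zero in a correctly specified model. The covariates listed in C5 (acute illness, hospital days, comorbidity) could absorb more if used. Only the unobserved part is at issue.

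**The size could be read too high.** Placing all attrition before a single follow-up gives 0.11-0.34 SD. But the contrast averages two follow-ups, and the documents do not say when the Table 5 attrition occurs; spreading it over three intervals to 6 months gives 0.06-0.17. Discharge of improving residents would bias towards no effect.

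**Staggering has some value.** It keeps one calendar event, such as a seasonal outbreak, from striking every unit's follow-up together. One could also read the stagger sentence as aimed at improvement unrelated to the intervention, raised earlier in the same paragraph; but it directly follows the attrition sentences, so its placement says otherwise.

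**Reporting.** A reader might infer that a null baseline test will be presented as clearing the result. The plan does not say so; it says alternative explanations will be considered.

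**Conclusion.** The point holds in a limited form. As written, C6 credits staggering with a protection that the timing of consent and baseline removes. A few losses may fall between baseline and launch, so the accurate statement is that essentially all attrition follows launch. The baseline comparison cannot tell harmful from harmless dropout, and in no case does it measure the bias.

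The plausible false improvement of roughly 0.09-0.23 SD rests wholly on assumed correlations, dropout strengths and attrition timing, and on worse residents being the ones who leave. It shows that the bias could be material against 0.60 SD; it does not predict that it will occur or in which direction. That staggering leaves the stated contrast unprotected, and that the test has no power against unpredicted change, do not depend on those values. The documents do not support the claim that the trial's result will be biased.

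**What to change.** 1. In C6, delete the stagger sentence, or replace it with a statement that essentially all attrition occurs after launch and that staggering does not separate it from exposure.
2. Keep the leaver-stayer baseline comparison as description only, not as evidence for or against attrition bias.
3. Add a delta-adjusted sensitivity analysis of the primary contrast: shift leavers' unseen scores by a range of amounts in both directions, and report the shift at which the conclusion changes.
4. As supportive evidence, compare change from the baseline to the last MDS record between leavers and stayers at the same quarter, by exit reason. This is possible only where a post-baseline record exists and exit reason is recorded. The documents do not say that exit reason is captured, and with quarterly MDS collection early leavers may have no later record. It is also only a proxy for actigraphy and PSQI, so item 3 carries the weight.

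Cost: a wording change and one extra analysis for items 1 to 3; item 4 may also need exit reason to be recorded. The downside is that a positive result will carry a stated tipping point and may look less robust.
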